4.6. Randomisation

Participants will be randomised in a 1:1 ratio to either Digoxin 62.5 – 250 µg od or Bisoprolol 1.25 – 15 mg od. The time between randomisation and commencement of trial therapy should be minimised (ideally <24 hours).

Randomisation will be provided by a computer generated programme at the Birmingham Clinical Trials Unit (BCTU), using a minimisation algorithm incorporating the following factors:

- Baseline EHRA (class 1/2a and class 2b/3/4)
- Gender (Male and Female)

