4.7. Sample size

Randomising 144 patients we can assume an 85% power to detect an effect size of half a standard deviation in a continuous outcome measure of QoL (two-sided alpha of 0.05).

A sample size of 160 patients would account for an estimated 10% loss to follow-up (including withdrawal and death prior to 12-month assessment).

There is some evidence from existing research to support the notion that the treatment effect could be this large. The mean SF-36 role-physical score from the rate-control arm of the RACE study was 47, with a 17% improvement with rate-control over time.² In another study, CCB resulted in 22% improvement in a proprietary symptom-checklist, compared to a non-significant 8% change in those assigned to beta-blockers (SD 10-points in both groups). These values are also consistent with a 17% improvement in SF-36 scores in a third trial, PIAF.³

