9.1. Covariate adjustment

In the first instance, intervention effects between groups for all outcomes will be adjusted for the baseline score (where appropriate), minimisation parameters (Gender, baseline EHRA) as well as age at randomisation and

baseline LVEF (as continuous variables). The minimisation variable EHRA is a categorical score with the following categories (1, 2a, 2b, 3, 4) and for minimisation, this score was categorised into (class 1, 2a) and (class 2b, 3, 4). However for the analysis we will be adjusting this variable in its original 5 categorical form.

The Bisoprolol arm will be used as a reference category for all model based analyses.

For some binary outcomes, sometimes the effect size to be estimated of interest is the relative risk rather than the odds ratio and so for these outcomes, a log-binomial model is often used. However there are convergence issues with this type of model and so if the log-binomial model fails to converge, a Poisson regression model with robust standard errors will be used to estimate the same parameters.⁷ If this also fails to converge, unadjusted estimates will be produced from the log-binomial model. It will be made clear in the final report why this occurred (e.g. not possible due to low event rate/lack of model convergence).

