If yes, then Diastolic dysfunction present

If no, then 

Does the patient have **two** or more of the following diastolic parameters?

- IVRT (ms) ≤ 65 ms
- Mitral Valve E deceleration time (ms) ≤ 120 ms
- Average E/e'(taken from lateral and septal wall) ≥ 11
- Pulmonary Vein diastolic deceleration time (ms) ≤ 220

If yes, then Diastolic dysfunction present

If no, then no diastolic dysfunction present

Change in European Heart Rhythm Association (EHRA) class

This outcome will be analysed as ordinal data initially but will also be analysed as a binary yes/no variable. The original classification for this score is in an ordinal scale and the categories are 1, 2a, 2b, 3, 4 where lowest category 1 indicates best outcome and highest category 4 indicates worst outcome. For this outcome to be coded as binary we will consider any one with a change in 2 categories from worse to better as “yes” for this outcome. Comparison will be made from baseline score to 6 months and baseline score to 12 months separately. EG: if a patient had a baseline EHRA class of 3a and by 6 months they had an EHRA class of 2a then this patient will be considered as “yes” for the classification of change in EHRA class. There may be some patients that cannot achieve a 2 point improvement in the score due to the score they originally had at baseline (i.e. if someone has a baseline score of 2a or below at baseline). These patients will be classed as not improved.

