- **Change in European Heart Rhythm Association (EHRA) class at 6 and 12 months**

The data for this outcome is categorical in nature and in 5 orderly categories; 1=None, 2a=Mild, 2b=Moderate, 3=Severe, 4=Disabling. This data is collected as baseline, 6 months and 12 months. This data will be summarised as number and percentage by treatment arm and time-point with respect to the EHRA class.

The analysis for this outcome will be conducted using an ordinal logistic regression model, where the outcome will be the EHRA class at follow up (with EHRA class 1 being the reference category) and independent variables in the model being the baseline EHRA class, treatment arm, gender, age at randomisation and baseline LVEF. An adjusted odds ratio and 95% confidence interval will be estimated from the ordinal logistic regression.

Higher EHRA class is considered to be a worse outcome and since the Bisoprolol arm will be used as a reference category in the model, higher values will indicate worse outcome for Digoxin arm.

Note: separate analysis will be done for 6 month and 12 month time-point.

We will also code this outcome as a binary “yes/no” variable where “yes” will be determined if patients had a 2 class improvement in the EHRA class from baseline. The full details for the computation of this are described in the data manipulations section 9.4.

The analysis for this outcome will be conducted using a logistic regression model, where the outcome will be the computed binary variable “yes/no” (with yes being the reference category) and independent variables in the model being treatment arm, gender, age at randomisation and baseline LVEF. An adjusted odds ratio and 95% confidence interval will be estimated from the logistic regression model.

Since we are modelling whether patients had an improvement from baseline and that the Bisoprolol arm will be used as a reference category in the model, higher values will indicate better outcome for Digoxin arm.

Note: again separate analysis will be done for 6 month and 12 month time-point.

Biomarkers

- **Change in NTpro-B-type natriuretic peptide (NTpro-BNP) levels**

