					Adjusted mean difference ¹ 95% CI	P-value ¹
Distance (metres)	Baseline	N Mean [SD] Min - Max			-	-
	6 months	N Mean [SD] Min - Max				
	12 months	N Mean [SD] Min - Max				

1-Adjusted for treatment arm, baseline score, all minimisation variables, age at randomisation and baseline LVEF

The Bisoprolol arm will be used as a reference category and so positive mean difference will indicate better outcome for Digoxin arm

Change in European Heart Rhythm Association (EHRA) class at 6 and 12 months

	Time point	Statistic	Digoxin	Bisoprolol	Ordinal Logistic regression model	
					Adjusted odds ratio ¹ 95% CI	P-value ¹
EHRA Class	Baseline	Class 1 Class 2a Class 2b Class 3 Class 4			-	-
	6 months	Class 1 Class 2a Class 2b Class 3 Class 4				
	12 months	Class 1 Class 2a Class 2b Class 3 Class 4				

1-Adjusted for treatment arm, all minimisation variables, age at randomisation and baseline LVEF.

Reference group for the treatment arm in the model is Bisoprolol arm.

Lower odds indicate better outcome so values <1 favours Digoxin arm.

2 class improvement in EHRA class at 6 and 12 months compared to baseline

EHRA Class	Time point	Statistic	Digoxin	Bisoprolol	Logistic regression model	
					Adjusted Odds Ratio ¹ 95% CI	P-value ¹
2 class improvement from baseline	6 months	No Yes				
	12 months	No Yes				

1-Adjusted for treatment arm, baseline score, all minimisation variables, age at randomisation and baseline LVEF

Reference group for the treatment arm in the model is Bisoprolol arm

Higher values indicate better scores so an odds ratio >1 favours Digoxin arm

Change in B-type natriuretic peptide (BNP) (NTproBNP) levels at 6 months

Secondary outcome	Time point	Statistic	Digoxin	Bisoprolol	Linear regression model	
					Ratio of geometric means ¹ 95% CI	P-value ¹
Log-transformed NTproBNP (ng/L)	Baseline	N Mean [SD] Min - Max			-	-
	6 months	N Mean [SD] Min - Max				
	12 months	N Mean [SD] Min - Max				

1-Adjusted for treatment arm, baseline score, all minimisation variables, age at randomisation and baseline LVEF

Reference group for the treatment arm in the model is Bisoprolol arm

Lower ratio indicates better scores so values <1 favours Digoxin arm

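### The binary two-class EHRA endpoint counts patients who cannot respond as not improved, and SAP 9.6 omits the baseline EHRA adjustment that SAP 9.1, Appendix D6 and protocol 12.3.2 call for, so two different odds ratios are specified

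*SAP*

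**What the plan says.** The EHRA scale has five ordered classes: 1, 2a, 2b, 3, 4. SAP 9.4 analyses it as ordinal first and then as a yes/no variable, with yes meaning an improvement of two classes from baseline. The same section recognises that a patient starting at 2a or lower has no room for this and rules: "These patients will be classed as not improved".

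The model for the binary endpoint is given in several places:

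- SAP 9.6: logistic regression, with "independent variables in the model being treatment arm, gender, age at randomisation and baseline LVEF". There is no baseline EHRA term.
- SAP Appendix D6, footnote to the two-class improvement table: "Adjusted for treatment arm, baseline score, all minimisation variables, age at randomisation and baseline LVEF". EHRA is one of the two minimisation variables, so it is in this model, and arguably twice.
- SAP 9.1, for all outcomes in the first instance: adjust for the minimisation factors. On EHRA it adds: "However for the analysis we will be adjusting this variable in its original 5 categorical form".
- Protocol 12.3.2: logistic or log-binomial models for dichotomous outcomes, where appropriate, adjusted for baseline score and every minimisation variable.

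SAP 9.1 has a fallback for non-convergence of the log-binomial model. There is none for logistic regression.

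**The concern.** Patients at baseline 1 or 2a are certain non-responders on either drug. A patient who goes from 2a to 1, the best class, is reported as not improved. Such patients can be enrolled: class 1/2a is a minimisation level (SAP 4.6) and a planned subgroup level (SAP 9.9), and protocol 4.1 sets an NYHA criterion but no EHRA criterion.

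Baseline class therefore largely decides who can respond, and 9.6 leaves it out of the model while the other three places put it in. An analyst who follows 9.6 and one who follows D6 with 9.1 will report different odds ratios for the same endpoint. Unless this is settled beforehand, the choice could be made after the data are seen.

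**Working it through.** **The plan's own figure.** No sample size or power is stated for this endpoint. The trial-level figure reproduces. SAP 4.7 gives "Randomising 144 patients we can assume an 85% power to detect an effect size of half a standard deviation", with "two-sided alpha of 0.05"; SAP 4.6 gives 1:1 allocation. Per arm: 2 × (1.960 + 1.036)² / 0.5² = 71.8, so 72 per arm and 144 in all (power 85.1%). With 10% loss, 144 / 0.90 = 160.

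**Step 1: size of the attenuation under 9.6.** Let s be the share at baseline 1/2a, equal in both arms, and let p_C and p_T be the response rates among patients at 2b/3/4. The all-patient rates are (1 − s)p_C and (1 − s)p_T. Then:

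- Risk ratio = p_T / p_C, whatever s is.
- Odds ratio = (p_T / p_C) × [1 − (1 − s)p_C] / [1 − (1 − s)p_T].

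As s rises, the odds ratio falls towards the risk ratio and no further. The documents do not give s, p_C or p_T, so all three are assumptions. With p_C = 0.20 and p_T = 0.40:

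| s | Rates | Difference | Risk ratio | Odds ratio |
|---|---|---|---|---|
| 0 | 20% v 40% | 20 points | 2.0 | 2.0 × 0.80/0.60 = 2.67 |
| 20% | 16% v 32% | 16 points | 2.0 | 2.0 × 0.84/0.68 = 2.47 |
| 40% | 12% v 24% | 12 points | 2.0 | 2.0 × 0.88/0.76 = 2.32 |
| 60% | 8% v 16% | 8 points | 2.0 | 2.0 × 0.92/0.84 = 2.19 |

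A second scenario, with p_C = 0.30 and an odds ratio of 2.0 among patients able to respond (p_T = 0.462, risk ratio 1.54), gives 1.85, 1.74 and 1.66 at s = 20%, 40% and 60%. A large simulation of the 9.6 model under that scenario gave 1.82, 1.75 and 1.66. Across control rates of 0.2 to 0.5, still with an odds ratio of 2.0, the attenuated value runs from 1.91 down to 1.45.

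**Step 2: behaviour of the D6/9.1 model.** Classes 1 and 2a have zero events by definition. The likelihood keeps rising as their fitted log-odds go to minus infinity, so the EHRA terms have no finite maximum likelihood estimate. In the limit these patients contribute nothing to the treatment effect.

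One simulated data set of 144 patients shows this (events/patients: class 1 0/5, 2a 0/44, 2b 19/51, 3 11/37, 4 2/7):

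- Five-category EHRA: the 2b coefficient, relative to class 1, was 5.8, 10.8, 15.8, 20.8 and 25.8 after 5, 10, 15, 20 and 25 iterations. Its standard error went from 9.9 to 217,530.
- Treatment log odds ratio in that model: stable at 0.513 (SE 0.451), odds ratio exp(0.513) = 1.67.
- Fit in the 51 + 37 + 7 = 95 patients at 2b/3/4 only, adjusted for class: 0.513 (SE 0.451), the same.
- SAP 9.6 model: 0.317 (SE 0.412), odds ratio exp(0.317) = 1.37.

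The two-level coding (1/2a v 2b/3/4) diverges in the same way. Entering five-category EHRA both as baseline score and as minimisation variable, a literal reading of the D6 footnote, gives a design matrix of rank 9 with 13 columns.

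**Step 3: power.** With 72 per arm, p_C = 0.30 and an odds ratio of 2.0, an unadjusted two-proportion comparison has power of 39%, 28% and 19% in all patients at s = 20%, 40% and 60%. In 2b/3/4 patients only it has 43%, 34% and 24%. With nobody at 1/2a it is about 52%. Most of the loss comes from having fewer patients able to respond; here the coding itself costs about 4 to 6 points.

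**The case against.** The case for leaving the plan alone is reasonable. The rule in 9.4 is open and pre-specified, and it keeps every randomised patient, in line with SAP 5.3. The proportion of all patients who improve by two classes is a legitimate estimand. SAP section 9 names 9.5 to 9.10 as the detailed source of methods, and D6 is a reporting template whose footnote recurs on most of its tables, so 9.6 may be meant to govern. The outcome is secondary, the binary version follows the ordinal one, and the magnitudes rest on assumed shares and rates.

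Much of this stands. The all-patient proportion deserves to be kept. The 1/2a share is unknown; if nobody enters there, both the attenuation and this separation disappear.

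The copied-footnote reading does not settle the matter. The D6 footnote for the neighbouring ordinal EHRA table is worded differently, so the footnotes were not simply repeated. Even if 9.6 governs, it omits a minimisation factor that SAP 9.1 and protocol 12.3.2 both say to adjust for, and gives no reason.

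Two stronger readings are tempting and should be resisted. A reader might infer that the D6 model cannot be estimated at all. Only the EHRA terms diverge; the treatment odds ratio remains identified. A reader might also infer that counting 1/2a patients as not improved favours one drug. These patients fail on both drugs, and minimisation on the same cut keeps their share similar in the two arms, so nothing in the documents supports a directional bias.

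**Conclusion.** The point holds as an inconsistent specification with odds-scale attenuation. The conflict between 9.6 and the other three places rests on the text alone. If any patients start at 1/2a, the two specifications target different treatment odds ratios: 9.6 gives one over all patients, attenuated towards the risk ratio, and D6 with 9.1 gives one from 2b/3/4 patients only.

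The size depends on assumptions. For a true odds ratio of 2.67 among patients able to respond, 9.6 would target 2.47 to 2.19 for a 1/2a share of 20% to 60%. The risk ratio does not change. The primary outcome, the sample size and the ordinal EHRA analysis, which uses all patients and adjusts for baseline class, are unaffected. It is worth correcting before analysis but does not threaten the trial's main conclusions.

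**What to change.** Make SAP 9.6 and the D6 footnote state one and the same model that conditions on baseline EHRA, entered once:

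- Fit the logistic model in patients at baseline 2b, 3 or 4. This is a minimisation level fixed before randomisation, so patients are still analysed in the arm to which they were allocated.
- Adjust for treatment, baseline class, gender, age and baseline LVEF. If class 4 may be sparse, specify 2b v 3/4 in advance and note it as an exception to the five-category rule in 9.1.
- Beside it, report the proportions in all patients, with 1/2a counted as not improved, and the risk ratio or risk difference. This keeps the intention-to-treat summary.
- Correct the worked example in 9.4, which uses a class 3a that is not on the scale.

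The same edit can say whether an improvement of more than two classes counts, and reconcile naming yes as the reference outcome category in 9.6 with reading an odds ratio above 1 as favouring digoxin.

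The change is to SAP wording only. The downside is a smaller denominator for this one supplementary endpoint. The patients left out carry no treatment information once baseline class is in the model.

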9.5. Analysis methods – primary outcome(s)

The primary outcome is the SF-36v2 physical component summary (PCS) score at 6 months.

The data for this outcome is continuous in nature and the computation for this score is described in the data manipulations section 9.4. The mean and standard deviation along with minimum and maximum values for the PCS score will be presented by treatment arm.

Data will be analysed using a linear regression model with outcome being the 6 months PCS score and independent variables in the model being the baseline PCS score, treatment arm, all minimisation variables, age at randomisation and baseline LVEF. An adjusted mean difference and 95% confidence interval will be estimated from the linear regression model and the p-value from the associated model will be produced. The Bisoprolol arm will be used as a reference category in the model and so higher values will indicate better outcome for Digoxin arm. A template for reporting the primary outcome is given in Appendix D5.

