Where poor quality acoustic windows limit accurate assessment of LV function, use of an intravenous contrast agent is recommended in participants without known allergy.

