12.3.1 Primary outcome analysis

The primary outcome for this trial is the continuous SF36 physical functioning domain score at 6 months. This outcome will be analysed using an ANCOVA model adjusting for treatment arm, baseline score and all minimisation variables. Results will be presented as difference in means and 95% confidence intervals.

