5.3. Analysis populations

All primary analyses (primary and secondary outcomes including safety outcomes) will be by intention-to-treat (ITT). Participants will be analysed in the intervention group to which they were randomised, and all participants shall be included whether or not they received the allocated intervention.

As a sensitivity analysis, a per-protocol analysis may also be carried out for the primary outcome if it is deemed a worthwhile investigation to further understand drug efficacy. See section 5.4 for how adherence information will be summarised. See section 9.10 for further details on any sensitivity analyses.

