9.10. Sensitivity analyses

Sensitivity analyses will be limited to the primary outcome only and will consist of:

- Per-protocol analysis (population described in sections 5.3 and 5.4)
- Adjust the final model for additional covariate of baseline apical heart rate
- SF36v2 questionnaire completed outside the pre-specified visit window of ± 4 week's

We have stated in the protocol that we will allow a ± 4 week's window for the follow up visits and so any questionnaires for SF36v2 at 6 months completed outside this time window will be excluded in this sensitivity analysis.

- Analysis to assess the impact of missing data (see below for method)

Missing data will be imputed using multiple imputation with chained equations in Stata 16 (or above). Stata's "MI" command will be used to carry out this analysis and the "regress" option will be used since the primary outcome is continuous data. 50 imputations will be generated for any missing data for primary outcome (i.e. SF36v2 PCS score at 6 months) and all minimisation variables (Gender, EHRA score), treatment arm, baseline PCS score and any other baseline data deemed appropriate will be used to aid the multiple imputation procedure. Imputed results will be combined using Stata's "mi estimate" command.

10. Analysis of sub-randomisations

N/A

11. Health economic analysis

Health economic analysis is planned for this trial and will be described separately in the health economic analysis plan by the health economist for the trial.

12. Statistical software

Statistical analysis will be undertaken in the following statistical software packages:

- Stata version 15 (or higher)
- SAS software, version 9.4 (or higher)

13. References

[figure not shown]

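### SAP 9.5 adds baseline LVEF to the primary regression with no rule for a missing value, so a patient with an observed 6-month PCS could drop out of the primary model

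*SAP*

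**What the plan says.** Protocol 12.3.1 gives the simpler primary model: "This outcome will be analysed using an ANCOVA model adjusting for treatment arm, baseline score and all minimisation variables". SAP 9.5 extends it, with "independent variables in the model being the baseline PCS score, treatment arm, all minimisation variables, age at randomisation and baseline LVEF". SAP 9.1 makes age and continuous baseline LVEF part of the adjustment for the modelled outcomes generally.

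On who is analysed, SAP 5.3 says that "all participants shall be included whether or not they received the allocated intervention". SAP 9.3 then bases the main analysis on the data actually received. It adds a sensitivity analysis of the primary outcome, partly so that the intention-to-treat principle is respected. That analysis is in SAP 9.10: "50 imputations will be generated for any missing data for primary outcome", which the same sentence identifies as the 6-month PCS. The minimisation variables, treatment arm, baseline PCS and other suitable baseline data serve to help the imputation. Baseline LVEF is not named there, either as a predictor or as a variable to impute.

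Neither document says what happens when a baseline covariate is missing. The retrieval of clinical echocardiograms in Protocol 8.7 concerns missing outcome scans, not baseline ones.

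**The concern.** A regression fitted to observed data uses only patients complete on the outcome and on every covariate. Each added covariate that can be missing is therefore a further way to lose a patient whose primary outcome was recorded.

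The other covariates carry little of this risk. Gender and EHRA class are needed to run the minimisation, and age follows from the date of birth. Baseline LVEF is different: it depends on an echocardiogram arranged at the baseline visit and reported by a core laboratory, and it is not needed to randomise. Protocol 9.6.2 recognises that image quality can be a problem ("Where poor quality acoustic windows limit accurate assessment of LV function"). Baseline PCS is exposed in the same way, but it is already in the protocol's model.

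At stake are precision, the completeness of the primary analysis relative to SAP 5.3, and the purpose of the sensitivity analysis. If that analysis imputes only the outcome, it omits the same patients. The loss would also be hard to see: the table in SAP Appendix D5 gives N for the PCS at each time point but not the N in the regression, and the baseline table in Appendix D2 has no N or missing row for ejection fraction.

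**Working it through.** **1. The plan's own figures.** Inputs from SAP 4.7: "Randomising 144 patients we can assume an 85% power to detect an effect size of half a standard deviation in a continuous outcome measure", "two-sided alpha of 0.05", and "A sample size of 160 patients would account for an estimated 10% loss to follow-up". Allocation is 1:1 (SAP 4.6).

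- Per arm: n = 2(z₀.₉₇₅ + z₀.₈₅)²/d² = 2(1.960 + 1.036)²/0.5² = 71.8, rounded up to 72, so 144 in total.
- Inflation: 144/0.90 = 160.
- Power at 144: 85.1% by the normal approximation, 84.6% by the noncentral t.

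The plan's 144, 85% and 160 reproduce. The inflation covers loss to follow-up only, with no allowance for missing covariates.

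**2. Who stays in the model.** Take 160 patients. Suppose 16 (10%) lack the 6-month PCS and 8 others lack only baseline LVEF; the 8 is an illustration.

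| Analysis | Patients in the regression |
|---|---|
| 6-month PCS observed | 160 − 16 = 144 |
| Main model, as written | 160 − 16 − 8 = 136 |
| Only the 6-month PCS imputed | 160 − 8 = 152 |
| Baseline LVEF filled in as well | 160 |

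A row count on one simulated data set with these numbers gave 144, 136, 152 and 160. Imputing the outcome brings back the 16 but not the 8.

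**3. Effect on power.** The documents give no rate of missing baseline LVEF, so 5% and 10% are assumptions. Analysed N = 144 × (1 − m), to whole patients. The noncentrality for two equal arms is 0.5 × √(N/4), with a two-sided 5% t-test and no covariate adjustment.

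| Assumed share missing, m | N | Noncentrality | Power (noncentral t) | Power (normal approximation) |
|---|---|---|---|---|
| 0% | 144 | 3.000 | 84.6% | 85.1% |
| 5% | 137 | 2.926 | 82.8% | 83.3% |
| 10% | 130 | 2.850 | 80.8% | 81.3% |

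On the noncentral t, the loss is 1.8 points at 5% and 3.8 points at 10%.

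**4. The same with adjustment.** If the covariates together correlate 0.5 with the outcome (an assumption), the residual SD is √(1 − 0.25) = 0.866 and the effective difference is 0.5/0.866 = 0.577 SD. Power is then 93.1%, 91.8% and 90.4% at N = 144, 137 and 130.

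**The case against.** The strongest reply is that the problem may never arise. The schedule of assessments marks the echocardiogram as a baseline procedure for every patient, without the parentheses used for conditional items. The Protocol 9.6.2 sentence on poor windows goes on to recommend a contrast agent, and that section lists several ways to obtain an LVEF. The absence of an N row for ejection fraction in Appendix D2 may mean it was expected to be complete. All this stands: no number missing can be claimed, and it could be zero.

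A reader might infer three stronger points, which the documents do not support.

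- *That the plan breaches its own intention-to-treat rule.* SAP 5.3 defines the set by allocation and regardless of treatment received, SAP 5.5 leaves room in how a participant is included, and SAP 9.3 and Protocol 12.3.3 openly declare an observed-data analysis. This is a disclosed complete-case approach with one unaddressed case.
- *That the treatment comparison would be biased.* Patients with unreadable scans may well differ from the rest, but the echocardiographer is to be blinded to treatment (Protocol 9.6), and nothing shows that missing scans would differ by arm.
- *That the imputation analysis is bound to exclude these patients.* SAP 9.10 specifies chained equations, which can handle several incomplete variables. The text does not forbid imputing LVEF; it does not plan it.

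Nor is adding a prespecified covariate a fault in itself, since Protocol 12.3 presents its analysis as an outline and leaves the detail to the SAP. The qualifiers in SAP 9 and 9.1, which make adjustment subject to feasibility and a first step, soften the commitment. They are not a rule, though: they leave the choice between dropping LVEF and dropping patients open until the data are seen.

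**Conclusion.** The gap is real and small. Taken together, SAP 9.5, 9.3 and 9.10 would remove from the primary model any patient with a 6-month PCS but no baseline LVEF or no baseline PCS, and no planned step restores that patient.

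The size is conditional. With nothing missing there is no effect. With 5% or 10% of 144 missing, both assumed, unadjusted power falls from 84.6% to about 82.8% or 80.8%. The adjusted model may have more power than this at every N, as step 4 illustrates, so the power loss is not the main argument. The main argument is that observed primary outcomes would be discarded for want of a covariate, when a prespecified sentence prevents it. The finding does not rest on bias between arms, which is not shown.

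**What to change.** Add to SAP 9.1: *A missing baseline covariate (LVEF or baseline score) is replaced by its mean over both arms combined, without reference to arm or outcome, so that every participant with a 6-month PCS enters the primary model.*

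Report the number of values replaced, and add the N in the regression to the Appendix D5 table. In SAP 9.10, list baseline LVEF and baseline PCS among the variables to be imputed alongside the 6-month PCS.

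The cost is one sentence, two variable names and one table entry. The downside is slightly less precise adjustment for the few patients with a replaced value. Because the replacement ignores arm and outcome, it does not bias the randomised comparison. If no baseline value is missing, the results do not change.
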